Protocol

CONIVAPTAN FOR THE REDUCTION OF CEREBRAL EDEMA IN INTRACEREBRAL HEMORRHAGE – A Safety and Tolerability Study

NSJC-1601 NCT03000283

Funded by United Hospital Medical Education and Research Committee

Principal Investigator: [name]

Co-Investigators: [name]
[name]
[name]

Research Nurse: [name]

Study Coordinator: [name], BS
[name], BA, CCRC

United Hospital, part of Allina Health
John Nasseff Neuroscience Institute, part of Allina Health
[name]
[name]
[contact]

TABLE OF CONTENTS

Section	Page
1. Research Goal	3
2. Specific Aims	3
3. Background	3
4. Significance	5
5. Preliminary Studies and/or Data	6
6. Research Design and Methods	6
6.1. Study Design	6
6.2. Inclusion/Exclusion Criteria	6
6.2.1. Inclusion Criteria	6
6.2.2. Exclusion Criteria	7
6.3. Subject Recruitment	7
6.4. Sample Size	7
6.5. Study Testing Location	8
6.6. Consent and Enrollment Process	8
6.7. Why a patient should participate in this trial	9
6.8. Treatment with Conivaptan	11
6.9. Primary Assessments	14
6.10 Secondary Assessments	15
7. Safety Variables	15
7.1. Risks and Benefits	16
7.2. Adverse Events	16
7.3. Serious Adverse Events	17
7.4. Adverse Events Reporting	17
8. Data Management	17
8.1. Data Reviewed	17
8.2. Data Entry & Database Completion	18
8.3. Data Sharing	19
9. Statistical Analysis	19
10. Study Oversight	19
11. IRB Review/Ethics/ Informed Consent	19
12. Confidentiality	20
13. References	20
14. Appendices	24

1. Research Goal

The goal of this study is to preliminarily determine/estimate feasibility and whether frequent and early conivaptan use, at a dose currently determined to be safe (i.e., 40mg/day), is safe and well-tolerated in patients with cerebral edema from intracerebral hemorrhage (ICH) and pressure (ICP). A further goal is to preliminarily estimate whether conivaptan at this same dose can reduce cerebral edema (CE) in these same patients. This study is also an essential first step in understanding the role of conivaptan in CE management.

Hypothesis: The frequent and early use of conivaptan at 40mg/day will be safe and well-tolerated, and also reduce cerebral edema, in patients with intracerebral hemorrhage and pressure.

2. Specific Aims

Aim 1: Evaluate the feasibility of the proposed study methods.

Subaim 1: Determine the efficiency of enrolling patients into the study. [Accomplished by tracking the number of patients asked to participate compared to the number of subjects enrolled into the study.]

Subaim 2: Determine the efficiency of obtaining all the study required data and information.

Aim 2: Estimate trends in the safety, tolerability, and efficacy of frequent and early conivaptan use (started within the first 48 hours from ICH symptom onset).

Subaim 1: Estimate if frequent and early use of conivaptan is safe and well-tolerated. [Based on previous work demonstrating conivaptan safety in other models, the working hypothesis is that early and frequent use will be well-tolerated, with few, if any, adverse events.]

Subaim 2: Evaluate the amount of adjunct osmotic therapy (i.e., mannitol, hypertonic saline) given throughout study period.

Subaim 3: Evaluate whether conivaptan reduces the extent of cerebral edema. [The working hypothesis is that early conivaptan use will reduce the presence of AQP4 and limit the development, and thus consequences, of CE.]

3. Background

Intracerebral hemorrhage (ICH) represents ~10-15% of all strokes in the United States (U.S.), numbering 50-70,000 cases per year, twice as common as subarachnoid hemorrhage (SAH), the 30 day mortality is ~40%, and greatest among the poor, elderly, black and Asian (Adams, 2005; Thomas et al., 1996). Only 20% of ICH patients are independent at 6 months. Only admission to a neuro-ICU, and the use of a CT scanner, have been shown to improve outcome from ICH (Thomas et al., 1996; Dinger & Edwards, 2001). With respect to cost, ICH represents 34% of years of potential life lost to stroke (Thomas et al., 1996). Per case, the cost is ~\$124,000, and the total lifetime cost for annual US cases >\$4B (Thomas et al., 1996).

Complicating ICH is the development of cerebral edema (CE). Worsening CE has been implicated in delayed neurological deterioration, and worse outcome, through the elevation of intracerebral pressure (ICP) (Mayer & Sacco, 1994). Elevations in ICP reduce the ability of blood to reach the

brain, exacerbating the injury and producing ischemia. The formation of peri-hematoma edema contributes to an increased volume of ~75% (Gebel et al., 2002). Animal models of ICH demonstrate a large peri-hematoma area that undergoes neuronal death characterized by increased water content and inflammation (Theix & Tsirka, 2007). Reduction of this edema may reduce the degree of neuronal death, decreasing hospital length-of-stay (LOS), and improving short-term outcome (Volbers et al., 2016).

Wide variability exists in the treatment of ICP and CE among intensivists (Hays et al., 2010). In part, this may be the function of training and/or experience. The use of mannitol, which elevates the osmolarity within the cerebral vasculature, promoting water movement across the blood-brain barrier and into the capillary system (Galton et al., 2011), is common, but is limited by its deleterious effects on renal function, fluctuations in intravascular volume, and pH. Most concerning is the slow elimination of mannitol from the cerebrospinal fluid (CSF) which may potentially require progressively higher doses, over time, to control ICP, and may result in rebound CE (Nau et al., 1997; McGraw & Howard, 1983). Increasingly, hypertonic saline (HS), which acts similar to mannitol, is being used to abate CE. However, this therapy has not demonstrated any survival or outcome benefit despite reductions in ICP (Bulger et al., 2010; Strandvik, 2009). And, currently, there is a national shortage of HS (FDA, 2010). A retrospective review of available data at Henry Ford Health System preliminarily demonstrates adverse effects on renal function with the use of HS ([name] et al., 2014). Further, anecdotal observations have noted changes in renal function and difficulty replacing free-water deficits (FWD) following aggressive antecedent use of HS. A known side-effect of HS therapy is hyperchloremia (HC). Chlorine is a potent renal vasoconstrictor potentially reducing blood flow, precipitating renal ischemia and reducing glomerular filtration rate (Wilcox, 1983; Gazitua et al., 1969). Finally, the use of HS may be associated with increased risk of blood-stream infections (BSI), and trends to increased risk of nosocomial and urinary tract infections (Bulger et al., 2010).

In sum, neurocritical care needs a therapy that can reduce the development of CE, potentially decreasing ICU LOS and possibly improving outcome. Could a single medication reduce the CE in ICH and improve the treatment variability found in this disease process? Conivaptan, a non-selective Arginine-Vasopressin (AVP) V_{1A}/V_2 antagonist that reduces aquaporin 4 production, thus promoting aqueresis, is approved for the treatment of euvolemic and hypervolemic hyponatremia (Cumberland Pharmaceuticals, 2014). The early use of conivaptan could potentially be used clinically to reduce CE by these means. Current clinical data in traumatic brain injury patients demonstrate conivaptan is safe and well tolerated using a single dose (20mg) to increase Na^+ in a controlled fashion to reduce ICP (Galton et al., 2011; Dhar & Murphy-Human, 2011). Further, additional work has demonstrated the safety and tolerability of conivaptan, in doses ranging from 10-80mg/day, in the neurocritical care population (Ghali et al., 2006; Zeltser et al., 2007; Verbalis et al., 2008; Annane et al., 2009; Murphy et al., 2009; Wright et al., 2009; Naidech et al., 2010; Human et al., 2012; Marik & Rivera, 2013).

AVP $V(1)$ receptor antagonism significantly reduces hemorrhagic brain edema in rat models (Rosenberg et al., 1992). Traumatic brain injury (TBI) research, using animal models, has demonstrated V_1 expression is increased in astrocytes and blood vessel endothelium during the first week following injury (Szmydynger-Chodobska et al., 2004). Experimental models have demonstrated AVP $V(1)$ receptor antagonism attenuates injury volume, and CE, through changes in aquaporin-4 (AQP4) expression (Liu et al., 2010). Although not the exclusive means for water flux in the brain, AQP4 is the predominant class of water channel in the brain (Yool et al., 2010; Zeynalov et al., 2008). For edema to occur, water must enter the astrocyte compartment. Water must pass from the capillary lumen and through the luminal, abluminal, and luminal perivascular endothelium. The perivascular pool appears, in both the influx and efflux of water, to be the rate limiting step (Zeynalov et al., 2008). Inhibition of water permeability, via reductions in AQP4, decreases ipsilateral hemispheric water content and may have therapeutic potential for CE in the clinical setting (Migliati et al., 2010; Rosenberg et al., 1992).

Animal models have demonstrated AQP4 expression increases within 6 hours from injury, peaks between 48-72 hours, and remains elevated over the first week (Li & Sun, 2003; Sun et al., 2009). This increased expression parallels brain water content (BWC) in hemorrhagic animal models. Antagonism of AVP V(1), in animal models of TBI and both hemorrhagic and ischemic stroke, is associated with parallel reductions of AQP4 expression and CE as measured by BWC (Liu et al., 2010; Taya et al., 2008; Trabold et al., 2008; Rosenberg et al., 1992).

Recently, bolusing of conivaptan (20mg) has been shown to lower ICP in hyponatremia following TBI and cerebral ischemia (Dhar & Murphy-Human, 2011; Galton et al., 2011). The authors reported improvements in cerebral perfusion pressure (CPP) and stable blood pressure, and a prolonged reduction in ICP. They theorize the V2 antagonism of conivaptan promotes free water loss to reduce BWC, and the V1 antagonism may improve cerebral blood flow (CBF) and reduce blood brain barrier permeability (Taya et al., 2008; Trabold et al., 2008; Dhar & Murphy-Human, 2011; Vakili et al., 2005; Kleindienst et al., 2006; Fernandez et al., 2001).

Given the enormous costs of ICH, problems with current therapies, and variability in treatment, there is an urgent need to identify a therapy that has a better safety and effectiveness profile compared to the currently used agents. Our central hypothesis is that through reductions in AQP4 expression, the early use of conivaptan will reduce CE while also being safe to the patient. Our long term goal is to show that early use of conivaptan in ICH will reduce CE, thus improving outcome and reducing the need for rescue therapies, ICU length of stay, and overall treatment cost. However, more data is needed to evaluate the dosing and amount of drug. With respect to conivaptan's efficacy in the correction of hyponatremia, a direct dose-response relationship exists (Onuoho et al., 2010). Further, this effect was more noted at milder degrees of hyponatremia, suggesting higher doses may be required to achieve a hypernatremic state (Onuoho et al., 2010). However, whether the reduction in CE parallels the relative changes in serum sodium remains to be determined. The objective of this proposal is to first establish whether conivaptan use, at a dose currently determined as safe (i.e., 40mg/day), can reduce CE. This proposed study is an essential first step in understanding the role of conivaptan in CE management. Prior to any mechanistic investigations, a fundamental understanding of dosing and toleration must occur. If this proof-of-concept study demonstrates the desired effect, work can take place identifying the optimal dosing and frequency needed for maximal effect. Later studies could ask questions on efficacy. Further, should such studies prove fruitful, mechanistic investigations using MRI and microdialysis could elucidate effects on membrane integrity, inflammation, and secondary cell injury.

4. Significance

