6.2.1 Major Inclusion Criteria

1. Age ≥ 18 years old and < 80 years.
2. Diagnosis of primary ICH ≥ 20 cc in volume.
3. Enrollment within 48 hours from initial symptoms.
4. Signed informed consent from the patient or obtained via their legally authorized representative (if the patient is not able to sign the informed consent themselves). The patient's decisional capacity to either provide or refuse consent will be determined using the Glasgow Coma Scale (GCS), which is being assessed at baseline and at 24 hours (+/- 6hrs) after enrollment. A potential study participant with a GCS > 14 will be asked to

provide their own initial study consent. A GCS \leq 14 would indicate the need to pursue consent via legally authorized representative. Patient and/or LAR must be English speaking.

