6.10 Secondary Assessments (Effectiveness)

- Reduction in CE as measured on CT. Goal is a 5-10% reduction in CE over time. Reduction will be measured both as absolute reduction, and as relative reduction, comparing the ratio of ICH to edema volume. The absolute edema reduction is more clinically relevant, while the ratio of ICH to edema volume has more research relevance, to aid in designing the next related studies.
- Outcome. mRS (Appendix 2) at discharge from ICU and from hospital stratified by APACHE II (Appendix 3), GCS (Appendix 4), and ICH Score (Appendix 5)
- Cost
 1. Length of stay in the neuro ICU.
 2. Need for EVD/bolt or surgical procedures (craniectomy, clot evacuation, VPS) for reduction/management of CE.
 3. Need for central venous lines, arterial lines, PICC lines, tracheostomy/PEGs.
 4. Duration on ventilator.
 5. Duration of EVD/bolt.

7. Safety Variables

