The study population consists of patients with ICH at risk for developing CE.

a. Primary Objective – Safety and Tolerability

An evaluation of the safety assessment parameters of each of the seven (7) subjects will be done by the PI and Co-I during the patient's care. Should events occur regarding the administration of conivaptan that raise safety concerns, the PI has the authority to withdraw the subject and/or halt the study pending further investigation.

b. Secondary Objectives

Several secondary hypotheses can be tested for data generated by this investigation:

1. Reduction in CE as measured on CT. Goal is a 5-10% reduction in CE over time.
2. Patient outcomes: the modified Rankin Scale (mRS) will be used to assess patient outcomes at hospital discharge. This scale assess functional deficits on a scale from 0 (no deficit) to 6 (death).
3. Cost of care: Several proximal measures will be used to assess cost, including length of stay in the ICU, the need for EVD/bolt or surgical procedures to reduce or manage CE, the need for lines (central venous, arterial, PICC) or tracheostomy/PEGs, and the number of patients that required ventilation.

Study Endpoints

1. Laboratory values: assessment will end at the completion of conivaptan administration (Day 3).
2. Long-term Outcome: Patients will be observed for three months, beginning at enrollment, to determine long-term outcomes of conivaptan treatment.

4. Investigation Plan

This a single-center, open-label prospective study which aims to evaluate the safety and tolerability of conivaptan in patients with ICH that are at risk for developing CE. The study will include 7 patients with a diagnosis of ICH that is ≥ 20 cc in volume, aged between 18 – 80 years. All patients will receive 20mg IV of conivaptan every 12 hours equaling 40mg/day over 2 days (4 doses total), in addition to the standardized ICH management.

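### The ICH-to-edema ratio is undefined at zero edema and rises when the hematoma grows: use edema over baseline ICH volume, and align the Protocol goal with the population enrolled

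*Protocol*

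**What the plan says.** Protocol 6.10 plans to measure edema reduction on CT in two ways: as an absolute change, and as a relative change "comparing the ratio of ICH to edema volume". Section 6.4 describes the same ratio, with hemorrhage volume first and edema volume second. The target is a 5–10% reduction over time. Section 6.10 calls the absolute change more clinically relevant and keeps the ratio mainly to help design later studies. Neither document gives a rule for zero or unmeasurable edema.

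On the population, the Research Goal (Protocol 1) is set "in patients with cerebral edema from intracerebral hemorrhage (ICH) and pressure (ICP", and Protocol 7.1.2 likewise speaks of patients with edema. The hypothesis is that the drug will "also reduce cerebral edema, in patients with intracerebral hemorrhage and pressure". The only lesion-related inclusion criterion is "Diagnosis of primary ICH ≥ 20 cc in volume", alongside "Enrollment within 48 hours from initial symptoms". None of the 4 inclusion and 11 exclusion criteria sets an edema or ICP condition. SAP section 3 states: "The study population consists of patients with ICH at risk for developing CE". SAP section 4 repeats this, referring to "conivaptan in patients with ICH that are at risk for developing CE".

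**The concern.** A relative measure of edema should move in one known direction when edema changes, stay put when something else changes, and exist for every patient in the single analysis set. Hemorrhage divided by edema meets none of these conditions. Hematoma expansion is itself a listed safety parameter (Protocol 6.9, neurologic tolerability, item 5), yet it pushes the ratio the same way as successful edema reduction, so harm can look like benefit. The reverse also holds: a shrinking clot lowers the ratio and can hide a real fall in edema. Because section 6.10 intends the ratio to inform the next studies, the distortion would carry forward.

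The population wording matters for interpretation. A result stated for patients with edema and ICP would describe a group that the criteria do not define and that the data may not identify in full.

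**Working it through.** The plan gives no numerical value for the ratio, and the sample size of 7 rests on precedent, time and budget, so there is no figure to reproduce.

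**Inputs.** Minimum ICH volume H = 20 cc (Protocol 6.2.1, item 2). Target reduction 5–10% (6.10). N = 7 (6.4). The background (Protocol 3) mentions an increase in volume of about 75% from peri-hematoma edema. I read this as edema relative to ICH volume, which is an assumption, giving E = 0.75 × 20 = 15 cc. I also assume that H in the ratio is the volume on the same scan as E, since 8.1 measures ICH volume serially.

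**1. Direction.** R = H/E = 20/15 = 1.33. A 5% edema reduction gives 20/14.25 = 1.40 and a 10% reduction gives 20/13.5 = 1.48. Success raises R.

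**2. Hematoma expansion.** Cutting E by a fraction d multiplies R by 1/(1 − d). Growth of H to H/(1 − d) does the same with edema unchanged. From 20 cc:
- d = 5%: 20/0.95 = 21.05 cc, growth of 1.05 cc.
- d = 10%: 20/0.90 = 22.22 cc, growth of 2.22 cc.

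This holds whatever the edema volume. Both volumes can even worsen: if H goes from 20 to 30 cc and E from 15 to 20 cc (assumed values), R = 30/20 = 1.50, above the 1.48 produced by a true 10% edema reduction.

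**3. Small denominators, H = 20 cc.**

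| Edema (cc) | ICH/edema | Edema/ICH |
|---|---|---|
| 15 | 1.33 | 0.75 |
| 5 | 4 | 0.25 |
| 1 | 20 | 0.05 |
| 0.1 | 200 | 0.005 |
| 0 | undefined | 0 |

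Entry is within 48 hours, while Protocol 6.7 puts the edema peak at 7–14 days, so the baseline scan precedes the peak.

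**4. How often could the baseline ratio be undefined?** The documents give no share p of patients without measurable baseline edema. For assumed p, the chance of at least one such patient in 7 is 1 − (1 − p)^7, and the expected number with edema is 7(1 − p):
- p = 1%: 6.8%; 6.93 of 7
- p = 5%: 30.2%; 6.65 of 7
- p = 10%: 52.2%; 6.3 of 7
- p = 20%: 79.0%; 5.6 of 7

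**5. Replacement.** Take edema at each scan over baseline ICH volume. With 15/20 = 0.75 at baseline, a 5–10% reduction gives 14.25/20 = 0.713 to 13.5/20 = 0.675. The case in step 2 where both volumes worsen gives 20/20 = 1.00. The measure falls when edema falls, rises when edema rises, ignores later hematoma growth, and equals 0 at zero edema.

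**6. Population.** The goal requires edema and ICP. The hypothesis names pressure and treats edema as the outcome. The criteria require neither, and the SAP says at risk. Baseline CT can show edema, but ICP cannot be checked in everyone: monitors are placed at the treating physicians' discretion (6.8), values are collected only when a monitor is in use (8.1), and Table 1, note a, lists identifying and correcting ICP among the pre-enrollment care steps.

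**The case against.** The ratio is one of two effectiveness measures in a seven-patient study that declares itself unpowered. The SAP does not use it: sections 5.2 and 5.3 report change in edema volume and call all evaluation descriptive. Its direction could be handled by a label, and the order of the two terms may be loose wording. With bleeds of at least 20 cc and the background's figure of about 75%, most baseline ratios may be well behaved. Some protection exists already: 6.9 limits the ICP comparison to monitored patients, section 9 plots edema for the 7 patients, and the SAP population fits the criteria.

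Most of this stands and limits the weight of the point. It does not remove the zero denominator or the confounding with hematoma growth. A label corrects the direction but cannot tell a smaller edema from a larger bleed.

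Three stronger readings are tempting, and the documents do not support them:
- **The study cannot speak to patients with edema.** Not requiring edema does not mean that patients lack it; even at an assumed 20% without it, 5.6 of 7 would be expected to have it. Aim 2, Subaim 3 also covers prevention, expecting that "early conivaptan use will reduce the presence of AQP4 and limit the development, and thus consequences, of CE", so a patient without baseline edema is still relevant.
- **Excluding serum sodium of 145 mmol/L or more removes patients already treated for edema.** No document says how many patients given hypertonic saline would reach that level before enrollment.
- **One extreme percent change would swamp the seven-patient mean.** Neither document plans to average individual percent changes, and the SAP reports medians and full range beside means.

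**Conclusion.** The point holds for the ratio and for the population wording. As written, the relative measure has no value at zero edema, grows without limit as edema approaches zero, and cannot separate edema reduction from hematoma expansion. At 20 cc, 1.05 to 2.22 cc of bleed growth imitates the whole target effect. That equivalence needs no assumed edema volume, only that the numerator is measured on the same scan; if the numerator is baseline ICH volume, the expansion problem disappears and the zero-denominator problem remains. The frequency of near-zero baseline edema is unknown, so the probabilities above are a range and not an estimate.

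The Protocol goal and the SAP describe different populations. The design does not ensure edema or raised ICP at entry, and it does not verify ICP in every patient. This is a matter of definition and interpretation for a secondary measure. Absolute edema change, the primary safety objective and the sample size are unaffected.

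**What to change.** 1. In Protocol 6.4 and 6.10, replace the ratio with edema volume at each scan divided by baseline ICH volume, which inclusion criterion 2 keeps at 20 cc or more. State which of the two ICH volume methods in 8.1 supplies the denominator. Report ICH volume separately at each scan, so that expansion is seen as expansion.
2. Keep absolute edema change as the more clinically relevant measure. Give percent change only for patients with measurable baseline edema, and state how many that is.
3. Restate the Protocol 1 goal as concerning patients with primary ICH of at least 20 cc at risk for cerebral edema, matching the criteria and SAP section 3. Limit any statement about ICP to patients in whom it was monitored.
4. If the relative measure is to be reported, add it to SAP 5.2 and 5.3 in the same form.

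The cost is wording only. All volumes are already planned, and no patient, scan or procedure is added. The price is a narrower stated claim.

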6.4 Sample Size

This study is looking to preliminarily evaluate the safety, tolerability, and efficacy (presence of moderate reduction in CE), and as a ratio of ICH volume to CE volume. Unfortunately, it is not powered to provide robust statistical evaluation of safety and tolerability, nor to detect differences in efficacy, due to time and budgetary limitations.

Seven (7) patients will be treated with conivaptan (40mg/day; four 20mg doses over a 2 day period) in addition to conventional medical means. This number of patients takes into account information in the conivaptan in TBI patients study by Galton et al (2011), use of glyburide in ICH by Sheth et al. (2014), as well as time and budgetary limitations.

The goal is to enroll all seven (7) patients within an 18-month period. This recruitment goal should be achievable since:

- 1) according to the PI's experience, (based on 2015 data) ~50-70 ICH patients (ICD-10-CM code 161.9) are admitted per year to United Hospital and
- 2) according to a recent electronic feasibility search, in the year 2015, 55 patients with a diagnosis of ICH were admitted to United Hospital. Of these patients, the PI determined that 9 would have been eligible for the study, based on the study's inclusion and exclusion criteria.

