- Participation in another study for ICH or intraventricular hemorrhage.
- ICH related to infection, thrombolysis, subarachnoid hemorrhage, trauma or tumor.
- Presence of HIV or active fungal infection that is known based on information in the EMR.

- Continued use of digoxin or amlodipine (as recommended by the manufacturer due to CYP3A inhibition).
- Active hepatic failure as defined by AST >160 units/L and/or ALT >180 units/L, or total bilirubin levels greater than four times normal levels (>4.8mg/dL).
- Serum Na⁺ ≥ 145 mmol/L (admission labs or any time prior to recruitment/enrollment).
- Unable to receive conivaptan based on contraindications indicated by the manufacturer.
- Pregnant or lactating females.
- Not expected to survive within 48 hours of admission, or a presumed diagnosis of brain death.

5. Statistical Methods

5.1: Study Subjects and Analysis Sets

All enrolled patients will be included in a single analysis set and data will be summarized using frequencies and percentages.

5.2: General Methodology

This study is looking to preliminarily evaluate the safety, tolerability, and efficacy of conivaptan treatment. Unfortunately, it is not powered to provide robust statistical evaluation of safety and tolerability, nor to detect differences in efficacy between subjects. As such, all analysis will be descriptive in nature. Categorical variables will be summarized using counts and percentages. Continuous variables will be summarized using descriptive statistics: number of patients, mean, median, and full range, as appropriate.

Statistical analysis will consist of:

- Descriptive analysis of patient characteristics
- Frequency of relevant complications and medical interventions
- Changes in CE volume

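### Aim 1 measures enrolment efficiency as a consent rate, which can overstate enrolment feasibility if suitable patients are not screened or approached, and the SAP carries no Aim 1 analysis

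*Protocol*

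**What the plan says.** Protocol section 1 puts feasibility first: "The goal of this study is to preliminarily determine/estimate feasibility". Section 2 makes it Aim 1, with two parts. Subaim 1, enrolment efficiency, is to be "Accomplished by tracking the number of patients asked to participate compared to the number of subjects enrolled into the study". Subaim 2 is to "Determine the efficiency of obtaining all the study required data and information", and no measure is given for it.

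Section 6.4 adds a recruitment target, "The goal is to enroll all seven (7) patients within an 18-month period", and its basis: "in the year 2015, 55 patients with a diagnosis of ICH were admitted to United Hospital", of whom "the PI determined that 9 would have been eligible for the study".

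On who is reached:

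- Section 6.3 limits screening to patients whom the investigators see in their usual Neuro-ICU practice.
- Section 6.6 plans to approach patients who satisfy the criteria, or their LAR, and requires consent within 48 hours of onset.
- Section 6.2.1 makes the 48-hour limit, signed consent and English speaking part of the inclusion criteria.

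Protocol section 9 contains no feasibility analysis. The SAP's objectives begin with "Primary Objective – Safety and Tolerability" and do not include feasibility. Neither do its analysis list (5.2) or its evaluation of objectives (5.3). SAP 5.1 states: "All enrolled patients will be included in a single analysis set".

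**The concern.** Enrolled over asked answers one question: of those invited, how many agreed? A feasibility aim also has to show how many suitable patients the hospital admitted and where the others were lost. In this design they can be lost before anyone is asked:

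- The patient is identified after 48 hours.
- The patient has a GCS of 14 or less and no LAR can be reached.
- Neither patient nor LAR speaks English.
- The patient is not under an investigator's care.
- The admission falls at a weekend, when section 6.6 lists only the PI and co-investigator for consent.

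None of these enters the planned ratio. The data plan does not capture them elsewhere either. Section 8.1 lists no screening or approach data, and section 6.6 assigns a subject number only after consent.

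Section 8.3 says the results will serve as preliminary data for a later controlled or dose-finding study. A consent rate read as an enrolment rate could lead that study to expect too many patients per site. With seven patients and an admitted lack of power for safety and efficacy, the recruitment experience is among the more usable outputs of this trial.

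**Working it through.** **Inputs (Protocol 6.4).** Target 7 patients in 18 months; 55 ICH admissions in 2015; 9 judged eligible; about 50 to 70 ICH admissions per year in the PI's experience. The sample size of 7 is pragmatic, so there is no power calculation to reproduce.

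**Step 1: the protocol's recruitment basis.**

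- Eligible share: 9/55 = 16.4%.
- Expected eligible in 18 months: 9 × 1.5 = 13.5. This exceeds 7, so the target is consistent with the protocol's own figures.
- Share of eligible patients that must enrol: 7/13.5 = 52%.
- At 50 admissions per year and the same share: 50 × 9/55 × 1.5 = 12.3, and 7/12.3 = 57%.
- At 70 per year: 70 × 9/55 × 1.5 = 17.2, and 7/17.2 = 41%.
- Planned pace: 7/18 = 0.39 enrolments per month.

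**Step 2: how the planned ratio relates to enrolled over eligible.** Let f be the share of eligible patients who are approached, so asked = f × eligible. Then

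enrolled/asked = (enrolled/eligible) / f,

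and the overstatement factor is 1/f. The documents do not give f, so the values below are assumptions. Each row has 7 enrolled out of 13.5 eligible, so enrolled/eligible is 52% throughout.

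| Share approached, f | Asked (13.5 × f) | Enrolled/asked | Factor 1/f |
|---|---|---|---|
| 1.0 | 13.5 | 52% | 1.0 |
| 0.9 | 12.15 | 58% | 1.1 |
| 0.8 | 10.8 | 65% | 1.25 |
| 0.7 | 9.45 | 74% | 1.4 |
| 0.6 | 8.1 | 86% | 1.7 |
| 0.52 | 7 | 100% | 1.9 |

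**Step 3: precision.** Exact (Clopper-Pearson) 95% intervals with 7 enrolled:

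- 7 of 8 asked: 88% (47% to 100%).
- 7 of 10 asked: 70% (35% to 93%).
- 7 of 14 asked: 50% (23% to 77%).

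The intervals overlap heavily. The useful information is the counts and the reasons for loss, more than any single percentage.

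**Step 4: sensitivity to the 18-month denominator.** Enrolment stops at 7. Suppose every eligible patient is approached and 7 of the first 8 consent. Recruitment then ends after 8/9 × 12 = 10.7 months, and both ratios are 7/8 = 88%. The 52% therefore applies only if recruitment runs the full 18 months.

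**Step 5: what eligible means here.** The 48-hour limit, consent and language are inclusion criteria. A patient first seen at hour 50 is ineligible by the protocol's definition, and so is missing from enrolled over eligible as well as from enrolled over asked. Changing the denominator to protocol-eligible patients would not show these losses. They appear only if eligibility is first judged on clinical criteria and the other three criteria are applied as separate, counted steps.

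**The case against.** The strongest reply is that section 6.6 already plans to approach patients who satisfy the criteria. If that is done, asked equals eligible, f is 1 and there is no overstatement. The section also provides for consent on any day of the week, consent by telephone and a consenting schedule, which reduces losses from staffing and LAR access. This stands: no document gives an approach share below 100%, so a bias cannot be asserted. It does not remove the gap, because the planned ratio could not show whether the intention was met, and patients outside the 48-hour, consent or language criteria remain uncounted even if it was.

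Other replies also have force:

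- Feasibility is not judged by this ratio alone. Subaim 2 covers data collection, and 7 patients in 18 months is a recruitment benchmark.
- The 9-of-55 figure can still be checked by repeating the electronic search and review, whatever Subaim 1 tracks.
- An enrolled-only analysis set is natural for descriptive safety summaries and is not in itself a fault.
- The SAP's primary objective is safety, and no safety or efficacy conclusion changes.

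A reader might infer that feasibility will in fact be overstated, for example as 88% against a true 52%. The documents do not support that. The contrast needs 8 approached out of 13.5, which no section states, and a full 18 months of recruitment. A reader might also describe patients lost to the 48-hour limit, consent or language as eligible but missed. Section 6.2.1 makes them ineligible.

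**Conclusion.** The concern holds as a limitation of the chosen measure. Subaim 1 as written is a consent rate. It can overstate enrolment feasibility if suitable patients are not screened or approached, and it does not show losses from the 48-hour limit, an unavailable LAR, language or staffing. With 7 enrolled out of 13.5 eligible, the overstatement runs from none to a factor of about 1.9.

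This rests on three assumptions: one year's eligibility count carries forward, the full 18 months are used, and the approach shares are as tabulated. A further caution is that a records search could not have applied signed consent, and the protocol does not say whether the 48-hour and language criteria were applied in reaching 9. If they were, the clinically eligible pool is larger and 52% is too high for that denominator.

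The absence of an Aim 1 analysis is judged on the text available, which lacks Protocol 6.5 and the opening of the SAP. The sections where such an analysis belongs (Protocol 9, SAP 3 and 5) are present and silent. The change is a cheap improvement. It does not correct an error in the safety or efficacy analysis.

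**What to change.** 1. **Redefine Subaim 1 as a flow.** Start from ICH admissions, for example by repeating the 2015 electronic search over the recruitment period. Then count screened, eligible on clinical criteria (applied before the 48-hour, consent and language criteria), approached, consented and dosed. Record one reason for each loss, including outside 48 hours, no LAR reached, language, not seen by an investigator, no staff available, and declined.
2. **Report three descriptive figures:** enrolled over clinically eligible, enrolments per month (planned 0.39), and the existing enrolled over asked. Give counts with each and exact intervals for the two proportions.
3. **Give Subaim 2 a measure:** the percentage of Table 1 items obtained, by item and visit, among patients still due that assessment.
4. **List items 1 to 3 in the SAP** as the descriptive Aim 1 analysis. State that the flow uses the screening log and admissions list, and leave the enrolled set for all other summaries.

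The cost is a short screening log, an admissions list and one extra table. The admissions list is needed because section 6.3 limits screening to the investigators' own patients, so a log kept at screening would not cover every ICH admission.
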